## 10.6 Superiority

The following superiority hypotheses will be tested if non-inferiority is demonstrated. By the closed testing principle there is no need for multiplicity adjustment.

**Ho:**  $CCS_{\text{Superior}} - CCS_{\text{X-STOP}} \leq 0$  (not superior)

**Ha:**  $CCS_{\text{Superior}} - CCS_{\text{X-STOP}} > 0$  (superior)

The posterior probability that  $(CCS_{\text{Superior}} - CCS_{\text{X-STOP}}) > 0$  will be determined using Beta(1,1) priors for 5-year  $CCS_{\text{Superior}}$  and for 5-year  $CCS_{\text{X-STOP}}$ . If the posterior probability of superior is at least equal to 0.95, then a superiority claim will be made.

## 10.7 Missing Data and Loss-to-Follow-Up

In order to best preserve an intent-to-treat philosophy, the primary analysis will be done on the mITT group. Those subjects who withdraw, or who are lost (LTFU) after randomization, will be included in the analysis using Bayesian imputation. This analysis will be the primary analysis, but recognizing that there is no way, statistically, to handle these subjects without possibly introducing bias, a tipping point analysis will be conducted.

The tipping point sensitivity analysis will be conducted in which missing values in each group are separately assumed to be either successes or failures. Treatment group differences will be computed based on all possible combinations of assigning success or failure to the primary overall success endpoint to the patients in the two groups. For example, one scenario will be that all missing Superior device observations are failures and all missing X-STOP observations are successes. The next scenario would have one success and the remaining missing values as failure for Superior and all missing X-STOP as successes. For each scenario, the Bayesian posterior probability of non-inferiority will be determined. These results will be plotted using a dot plot with the number of missings assumed as failures for Superior on the x-axis and the number of missing assumed as failures for controls on the Y-axis. The dots will be color coded to indicate whether or not the primary statistical conclusion changes under each individual scenario. If the fraction of scenarios in which the statistical conclusion changes is small, the primary results will have been shown to be robust against assumptions concerning missingness.

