### **5.2 Study Endpoints**

#### **5.2.1 Composite Endpoint (Primary) – Individual Patient Success**

Subjects will be evaluated for success at each follow-up interval through 60 months. The primary study endpoint is the rate of overall subject success at the 60 month follow-up visit. An individual subject will be considered a success if they meet all of the following conditions at the 60 month follow-up:

Clinically significant improvement in outcomes compared to baseline, as determined by meeting the following:

- At least two of three domains of the Zurich Claudication Questionnaire (ZCQ)
  - Improvement in physical function by  $\geq 0.5$  points
  - Improvement in symptom severity by  $\geq 0.5$  points
  - “Satisfied” or “somewhat satisfied” as defined by a score of  $\leq 2.5$  points on the patient satisfaction domain
- No re-operations, revisions, removals or supplemental fixation at the index level(s)
- No major implant- or procedure-related complications:
  - No dislodgement, migration, or deformation
  - No new or persistent worsened neurological deficit at the index level
  - No spinous process fractures
  - No deep infection, death, or other permanent device attributed disability
- No clinically significant confounding treatments:
  - No epidural injections or nerve block procedures at index level, spinal cord

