## 9.3 Subsequent Surgical Interventions

If the patient requires a subsequent surgical intervention at the index level(s), the Investigator should exit the patient from the study and document the reason on the End of Study CRF. The patient should be followed until discharge from post-operative care or resolution of any adverse events up to a maximum of 30 days. Subsequent surgical interventions are defined as:

- A revision is a procedure that adjusts or in any way modifies or removes part of the original implant configuration, with or without replacement of a component. A revision may also include adjusting the position of the original configuration.
- A removal is a procedure where all of the original system configuration are removed with or without replacement.

- A reoperation is any surgical procedure at the involved level(s) that does not include removal, modification, or addition of any components to the system.
- A supplemental fixation is a procedure in which additional instrumentation not under study in the protocol is implanted (e.g., supplemental placement of a rod/screw system or a plate/screw system).

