#### 10.2 Primary Outcome

The *treatment arm* (Superior® ISS) is compared to a control comprising surgical implantation of the X-STOP® IPD® device. The primary efficacy analysis is a responder analysis at 60-months post-op where a subject is a responder if each of the following are satisfied:

- Clinically significant improvement in outcomes compared to baseline, as determined by meeting the following for at least two of three domains of the Zurich Claudication Questionnaire (ZCQ):
  - Improvement in physical function by  $\geq 0.5$  points
  - Improvement in symptom severity by  $\geq 0.5$  points
  - "Satisfied" or "somewhat satisfied" as defined by a score of  $< 2.5$  points on the patient satisfaction domain
- No re-operations, revisions, removals or supplemental fixation at the index level(s)
- No major implant or procedure-related complications defined as:
  - No dislodgement, migration, or deformation
  - No new or persistent worsened neurological deficit at the index level
  - No spinous process fractures
  - No deep infection, death, or other permanent device attributed disability
- No clinically significant confounding treatments:
  - No epidural injections or nerve block procedures at index level, spinal cord stimulators or rhizotomies

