### 10.4 Analysis Populations

The study contains two treatment arms with patients receiving either the Superior® ISS or the X-STOP® IPD® device. The following subject groups or analysis populations will be used to complete the analysis of data:

*Modified Intent-to-treat* patient population (mITT): The mITT patient population will include all patients randomized, and with an anesthesia start time recorded, where patients will be classified by the group in which they are randomized, regardless of the treatment received.

*Per protocol* patient population (PP): The PP patient population will include all subjects with 60-month follow-up data and no major protocol deviations and subjects that failed before 60 months and subsequently did not complete 60 months.

The primary efficacy analysis will be conducted on the mITT patient population. Secondary efficacy analyses will be done on the PP population. All safety data will be analyzed based on the mITT patient population.

The numbers of patients in the mITT analysis set included 190 patients randomized to Superior® and 201 patients randomized to the X-STOP® IPD® Control group. Eight (8) Superior® patients and 12 X-STOP® IPD patients are from 2 sites that are not participating in the PAS. This reduces the analysis set to 182 Superior® and 189 X-STOP® IPD®, respectively. Assuming 85% follow-up for the primary effectiveness endpoint at Month 60, there will be 155 Superior® patients and 161 X-STOP® IPD patients included in the primary non-inferiority evaluation.

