**H0:  $CCS_{\text{Superior}} - CCS_{\text{X-STOP}} \leq -0.10$  (inferior)**

**Ha:  $CCS_{\text{Superior}} - CCS_{\text{X-STOP}} > -0.10$  (not inferior)**

At 2-years, follow-up compliance was 97% and 95%, and the observed overall success rates were 51.9% (95/183) and 49.7% (93/187) for Superior® ISS and X-STOP® IPD®, respectively. For the purpose of sample size analysis it was initially assumed: a) that at 5-years, follow-up compliance would be 85% in both groups (i.e., 155 Superior® and 161 X-STOP® IPD®); b) a device group difference equal to that observed at 2-years (i.e., 2.2%); and c) at 5-years 40% of Superior® ISS would achieve CCS (and so 37.8% is assumed for X-STOP® IPD®). In keeping with the original design, these hypotheses will be tested by determining the Bayesian posterior probability that  $(CCS_{\text{Superior}} - CCS_{\text{X-STOP}}) > -0.10$ .

If the Bayesian posterior probability is at least equal to 0.95, then the hypothesis that Superior® ISS is non-inferior to X-STOP® IPD® at 5-years will be accepted. Non-informative beta(1,1) priors were assumed for both groups. With these assumptions, power is 73% and type 1 error is equal to 0.05. However, updated Month 36 results reflect a device group difference equal to 5.7%. Conservatively assuming a 5% difference, power increases to 87% and remains above 80% for device group differences larger than about 3.5%.

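### Section 10.7 judges robustness by the share of equally weighted tipping-point scenarios that flip, which does not show whether plausible missing outcomes would overturn non-inferiority

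*Combined protocol and SAP*

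**What the plan says.** Section 10.7 makes the mITT analysis primary. Patients who withdraw or are lost "will be included in the analysis using Bayesian imputation". A tipping-point analysis follows, in which missing outcomes in each arm are set to every possible number of successes and the posterior probability of non-inferiority is recomputed each time. On the resulting plot, "The dots will be color coded to indicate whether or not the primary statistical conclusion changes under each individual scenario". The section then gives its criterion: "If the fraction of scenarios in which the statistical conclusion changes is small, the primary results will have been shown to be robust". It gives no cut-off for *small*, no weighting of scenarios and no plausible region.

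Section 10.5 supplies the decision rule: non-inferiority is accepted if the posterior probability that the difference exceeds -0.10 is at least 0.95. On priors it says: "Non-informative beta(1,1) priors were assumed for both groups". Section 10.4 plans the evaluable numbers: "Assuming 85% follow-up for the primary effectiveness endpoint at Month 60", 155 Superion and 161 X-STOP patients enter the non-inferiority evaluation.

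**The concern.** The grid and plot are sound. The difficulty is the summary drawn from them. The scenario in which every missing Superion patient fails and every missing X-STOP patient succeeds counts exactly as much as one close to the observed rates. The share therefore depends on how much of the grid lies in remote corners, and hence on how many patients are missing.

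The label *robust* is at stake. A well-supported result can look fragile, a result exposed to a two-sided adverse pattern can look safe, and two readers can reach opposite verdicts from one grid because *small* is undefined.

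**Working it through.** **Inputs.** Margin -0.10, threshold 0.95, Beta(1,1) priors, rates 40% and 37.8%, 155 and 161 completers (Section 10.5). Analysis set 182 and 189 (Section 10.4). Missing: 182 - 155 = 27 and 189 - 161 = 28. Scenarios: 28 x 29 = 812. The missing counts and all rate departures below are assumptions.

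**The plan's own figure.** Posterior = P(pS - pX > -0.10), with pS ~ Beta(1 + xS, 1 + nS - xS) and pX likewise. Enumerating both binomials at 155/161 gives power 74.3% for 40% versus 37.8% (stated 73%; normal approximation 71.9%) and 88.1% for a 5-point difference (stated 87%; normal approximation 86.7%). The stated figures are reproduced to within 2 points.

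**Share against chance.** Each of the 812 scenarios is completed to 182/189 and flips if its posterior is below 0.95.
- Share = flipping scenarios / 812.
- Chance = sum over flipping scenarios of P(i successes among 27) x P(j successes among 28). The weights are beta-binomial for missing-at-random (MAR), and binomial at the observed rate plus the stated shift for departures.

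| Observed, Superion vs X-STOP | Available-case posterior | Share | Chance, MAR | -10/+10 | -20/+10 | -20/+20 |
|---|---|---|---|---|---|---|
| 62/155 vs 61/161 (planning) | 0.987 | 234/812 = 28.8% | 3.5% | 33% | 60% | 87% |
| 62/155 vs 57/161 | 0.996 | 156/812 = 19.2% | 0.1% | 3% | 11% | 36% |
| 62/155 vs 56/161 | 0.998 | 139/812 = 17.1% | 0.03% | 1% | 5.4% | 24% |
| 62/155 vs 65/161 (marginal) | 0.961 | 328/812 = 40.4% | 25.9% | 80% | 95.5% | 99% |

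Shifts are in percentage points, missing Superion first, missing X-STOP second. At planning rates with binomial weights and no shift, the chance is 2.5% instead of 3.5%.

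At planning rates the share is about 8 times the MAR chance (28.8/3.5) and about half the -20/+10 chance (28.8/60). In the second row it is about half the -20/+20 chance (19.2/36).

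**Dependence on follow-up** (planning rates, approximately):

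| Follow-up | 95% | 90% | 85% | 80% | 75% |
|---|---|---|---|---|---|
| Share | 6% | 18% | 29% | 35% | 38% |
| Chance at observed rates | 0.04% | 0.4% | 2.5% | 4.9% | 8.6% |
| Chance, -20/+10 | 1.4% | 18% | 60% | 83% | 95% |

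The share is not a fixed multiple of either chance.

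**Where the planning result tips.** The fewest Superion successes (of 27) that keep non-inferiority, by X-STOP successes (of 28): 2 at 9, 4 at 11, 6 at 13, 9 at 15. The flipping scenario nearest the expected counts is 7/27 versus 14/28, completed totals 69/182 versus 75/189, posterior 0.94997. That is 26% success among missing Superion patients (40.0 - 25.9 = about 14 points worse than observed) and 50% among missing X-STOP patients (50.0 - 37.9 = about 12 points better).

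**Averaged posterior** (completed-data posterior averaged over imputations), planning rates: 0.967 with missing Superion 15 points worse alone; 0.941 if missing X-STOP are also 10 points better. Shifting one arm or both changes the verdict.

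**Imputation by arm with Beta(1,1) only.** Averaging p(pS, pX | observed, missing) over p(missing | observed) returns p(pS, pX | observed). Both calculations give 0.98693 at planning rates, so this form of imputation adds nothing to the available-case analysis.

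**The case against.** The plan never calls the fraction a probability. It displays every scenario, admits that no method for these patients is free of possible bias, and leaves the 0.95 rule untouched. All of that stands: the criticism is of one sentence used as a criterion.

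The share also errs mainly on the cautious side. With 62/155 versus 57/161, shifting missing Superion patients alone by 20 points gives a chance of only about 2.5%, against a share of 19.2%. A reader might infer that the rule generally gives false reassurance. The calculations do not support that: understatement at that result appeared only when both arms departed strongly.

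Missingness may be lower than assumed. At two years 183 of 190 and 187 of 201 had outcomes, so 7 and 14 were missing. With those counts (70/175 versus 66/175 assumed) the share is 10.0% and the chance 0.09%. The mismatch remains but matters less.

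If combinations were counted over individual patients (2 to the power 55) instead of counts per arm, the planning share would be 3.6%. The worked example and the plot axes point to counts. Under the patient-level reading every missing patient would in effect have a 50% success rate, which is no better founded.

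Finally, a range of departures is itself a judgement. True, but it can be stated, justified and fixed beforehand.

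**Conclusion.** The concern holds for the robustness criterion. With 27 and 28 missing at planning rates, one share of 28.8% accompanies chances of a changed conclusion from about 3.5% (missing-at-random) to about 60% (20 points worse, 10 better). The share usually overstates fragility and can understate it under two-sided adverse departures. These sizes rest on 85% follow-up and on the assumed departures; the documents give no dropout pattern.

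Three stronger readings are not supported:
- **The primary conclusion is invalid.** The criterion labels a sensitivity analysis and does not enter the 0.95 rule.
- **The primary imputation is biased, or is an available-case analysis under another name.** Section 10.7 states no imputation model, and Section 10.5 gives Beta(1,1) as the prior on the success rates. This is a missing detail, not a demonstrated bias.
- **Patients who leave after index-level surgery are imputed as possible successes.** Section 9.3 says "the Investigator should exit the patient from the study and document the reason on the End of Study CRF", but Section 10.2 already makes such surgery a composite failure, and Section 10.7 imputes only those who withdraw or are lost.

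**What to change.** Keep the full grid and dot plot and replace the sentence on the fraction of scenarios with three elements:
1. Report the tipping boundary as success rates among missing patients in each arm, including the flipping scenario nearest the imputed rates (at planning rates about 7/27 versus 14/28). Show neighbouring scenarios, since that one lies almost exactly at 0.95 and 8/27 versus 14/28 gives 0.960.
2. Report the averaged posterior over a set of departures that moves both arms, for example missing Superion 5, 10 and 15 points worse combined with missing X-STOP unchanged and 5 and 10 points better. Fix the set before the Month-60 data are analysed.
3. Call the result robust only if the averaged posterior stays at or above 0.95 over that range, with the sponsor justifying its limits.

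Clarifications only:
- State the Bayesian imputation model before analysis. One option is Month-60 success within arm given last observed success or ZCQ status. The data exist, since Section 5.2.1 says "Subjects will be evaluated for success at each follow-up interval through 60 months".
- Reconcile the 155/161 count in Section 10.4 with the imputation to the mITT set in Section 10.7.

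The cost is SAP wording and modest programming, with no new data. The downsides are that the range of departures is a judgement, and that imputing from earlier status assumes it explains dropout, which is a reason to keep the full grid.

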## 10.8 Stratified Analysis for Multiple-Level Analysis

A logistic regression analysis will be conducted with level (one-level and two-level) and treatment as additive factors. Additionally an interaction effect between level and treatment will be included.

## 10.9 Secondary Endpoints

Secondary continuous effectiveness endpoints will be summarized by treatment group over time and as changes over time with descriptive statistics including means, standard deviations, median, minimum and maximum values. Secondary categorical effectiveness endpoints will be summarized by treatment group over time using counts and percentages. Descriptive effect size measures such as standardized mean differences will be presented as an aid in comparing magnitudes of groups differences across endpoints measured on different scales. Secondary endpoints analyses may also include other traditional frequentist confidence intervals and p-values for superiority.

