### 5.2.2 Secondary Endpoints

The secondary endpoints of this investigation are:

- To demonstrate the superiority of Superior® ISS to X-STOP® IPD® in effectively treating moderately impaired LSS patients as measured by 60 months postoperative overall success rates
- VertiFlex® Patient Satisfaction Survey – percent of patients scoring  $\leq 2.5$  on a 4 point scale
- Oswestry Disability Index (ODI) Version 2– compared to baseline, 15 point improvement (reduction in score) is considered clinically significant
- Visual Analogue Scale (VAS) - compared to baseline, an improvement in leg and/or back pain of 20 mm (on a 100 mm scale) is considered clinically significant
- To evaluate generic health status pre- and postoperatively using the SF-12 Short Form Health Survey, Version 2
- To evaluate maintenance of distraction defined by  $\leq 4$  mm of measurable decrease in the posterior disc space height on successive radiographs obtained at 6 weeks and 60 months postoperatively

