### 6.5.2 Baseline Assessment

The following baseline assessments were performed:

Subject Self-Report Questionnaires will be administered: 

• Zurich Claudication Questionnaire (ZCQ)

• Visual Analogue Scale (VAS)

• SF-12 version 2 Health Related Quality of Life

• Oswestry Disability Index (ODI)

Demographic/History and Physical Assessment: 

• Date of birth, race, ethnicity

• Gender, weight, height, and body mass index (BMI)

• Work status

• Nicotine use

• Leg and back pain

• Medical treatment

• Previous surgeries, co-existing diseases, any disabilities and concomitant medication

Neurological Assessment: 

• Muscle strength

• Sensory and Reflexes

• Range of motion

• Palpation of pulses

• Straight leg raise

• Femoral Stretch

Radiographic studies performed within 3 months of baseline: 

• Standing Anterior/Posterior Lumbar Spine view

• Lateral Lumbar Spine view

• Flexion/Extension Lateral Lumbar Spine views

• MRI or CT Scan

• DEXA Scan (If indicated)

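### Section 10.9 plans no baseline-adjusted comparison of ODI, VAS and SF-12 between arms, although the baseline scores are collected

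*Combined protocol and SAP*

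**What the plan says.** Section 10.9 is the only analysis text for the continuous secondary outcomes. It says: "Secondary continuous effectiveness endpoints will be summarized by treatment group over time and as changes over time with descriptive statistics". It continues: "Descriptive effect size measures such as standardized mean differences will be presented". Inference is optional: "Secondary endpoints analyses may also include other traditional frequentist confidence intervals and p-values for superiority". No model, baseline covariate or analysis visit is named. Categorical secondary endpoints get counts and percentages.

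Section 5.2.2 defines the endpoints. For ODI: "compared to baseline, 15 point improvement (reduction in score) is considered clinically significant". For VAS: "compared to baseline, an improvement in leg and/or back pain of 20 mm (on a 100 mm scale) is considered clinically significant". For SF-12 it gives no threshold: "To evaluate generic health status pre- and postoperatively using the SF-12 Short Form Health Survey, Version 2".

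The baseline scores exist. Section 6.5.2 opens with "The following baseline assessments were performed" and lists ZCQ, VAS, SF-12 and ODI. Section 6.5.4 and Appendix A repeat the questionnaires at nine follow-up visits from 6 weeks to 60 months. Elsewhere in the statistical section, baseline severity appears only in the descriptive stratified poolability analyses of 10.11.

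Two other sections bear on the remedy. Section 9.3 has patients exited after a subsequent surgical intervention at the index level, with at most 30 days of further follow-up. Section 10.4 puts the primary efficacy analysis on the mITT set and secondary efficacy analyses on the per-protocol set.

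**The concern.** In a randomized comparison of a score also measured at baseline, there are three usual estimates of the group difference: raw follow-up means, mean changes from baseline, and follow-up means adjusted for baseline. The raw comparison ignores baseline. The change comparison subtracts all of it, which over-corrects when the correlation is below 1 (with equal SDs). The adjusted comparison subtracts the fraction that the data support and, in large samples, is no less precise than either.

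Section 10.9 offers the first two and not the third, and does not say which is the result. The two differ by exactly the observed baseline difference between arms. In addition, a patient with earlier scores but no Month-60 score adds nothing to a Month-60 summary. The imputation and tipping-point rules of 10.7 are written for the primary endpoint.

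At stake are the supporting comparisons on disability, pain and quality of life: their effect sizes and any optional intervals and p-values.

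**Working it through.** **Inputs.** The documents state no SD, correlation, precision or power for ODI, VAS or SF-12, so there is no plan figure to reproduce on this point. The stated powers (73% and 87%) concern the primary composite and do not bear on it. The patient numbers in 10.4 do reproduce: 0.85 × 182 = 154.7, or 155, and 0.85 × 189 = 160.65, or 161. The correlation r between baseline and Month-60 score is assumed, mainly over 0.2 to 0.6. "Changes" in 10.9 is read below as change from baseline.

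**Variance of the group difference, equal SDs.** In units where the raw Month-60 comparison has variance 1:

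- raw: 1
- change from baseline: 2(1 − r)
- adjusted for baseline: 1 − r²

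The reduction from adjustment is r² against raw and 1 − (1 + r)/2 = (1 − r)/2 against change.

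| r | change | adjusted | cut vs raw | cut vs change | cut vs better of the two |
|---|---|---|---|---|---|
| 0.2 | 1.60 | 0.96 | 4% | 40% | 4% |
| 0.3 | 1.40 | 0.91 | 9% | 35% | 9% |
| 0.4 | 1.20 | 0.84 | 16% | 30% | 16% |
| 0.5 | 1.00 | 0.75 | 25% | 25% | 25% |
| 0.6 | 0.80 | 0.64 | 36% | 20% | 20% |

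On the standard-error scale, the cut against change scores is 1 − √0.60 = 23% at r = 0.2 and 1 − √0.80 = 11% at r = 0.6. Against raw values it is 1 − √0.96 = 2% and 1 − √0.64 = 20%.

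With 155 and 161 patients, the 95% half-widths in SD units are 0.221 (raw), 0.279 (change) and 0.216 (adjusted) at r = 0.2. At r = 0.6 they are 0.221, 0.197 and 0.176.

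**Unequal SDs.** Entry criteria can narrow the baseline range. Suppose the baseline SD is 0.7 of the Month-60 SD (an assumption). Then the change variance is 1 + 0.49 − 1.4r = 1.49 − 1.4r, while the raw and adjusted variances stay at 1 and 1 − r².

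- r = 0.2: 0.96/1.21, a cut of 21% against change; the raw comparison is the better one, and the cut against it is 4%
- r = 0.4: 0.84/0.93, a cut of 10%; change is the better one
- r = 0.6: 0.64/0.65, a cut of 2%; change is the better one

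**Chance imbalance, equal SDs.** The SD of the baseline difference is √(1/155 + 1/161) = 0.113 SD units, so 95% of trials fall within ±1.96 × 0.113 = ±0.22. An imbalance d leaves r·d in the raw comparison and −(1 − r)·d in the change comparison. At d = 0.22:

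- r = 0.3: +0.07 (raw) and −0.15 (change)
- r = 0.6: +0.13 (raw) and −0.09 (change)

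**The case against.** The strongest reply is that 10.9 is a descriptive plan. It commits to no test on ODI, VAS or SF-12, and no claim rests on them. The non-inferiority and superiority claims rest on the composite. This stands, and it limits the point to supportive results.

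A reader might infer that the collected baseline scores go unused. The documents do not support that. Change scores use them, and so do the 15-point ODI and 20 mm VAS criteria. What is missing is baseline as a covariate. The responder rates are a separate summary that an adjusted model of the continuous scores does not replace.

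A reader might also take 20 to 40% as the precision lost. That is a variance figure, against change scores only, and it depends on an assumed correlation and equal SDs. Section 10.9 also reports raw values, against which the loss at r = 0.2 is 4%.

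Nor is chance imbalance a bias. Under 1:1 randomization it averages to zero, and a valid unadjusted standard error already allows for it. What remains is that the two planned comparisons move in opposite directions for the same imbalance.

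Finally, a repeated-measures model has a weakness of its own here. Patients exited under 9.3 lack later scores because they needed further surgery. A missing-at-random model would in effect predict their Month-60 scores from patients who stayed in follow-up, which could flatter an arm with more reoperations. This objection stands and shapes the fix.

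**Conclusion.** The point holds in a limited form. Section 10.9 compares continuous ODI, VAS and SF-12 scores only through unadjusted raw values, changes and standardized mean differences, and a better estimate is available from data already collected.

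Under equal SDs and r of 0.2 to 0.6, the variance gain is 40 to 20% against change scores, 4 to 36% against raw values and 4 to 25% against the better of the two. Neither the correlation nor the SDs can be checked from the documents. With a smaller baseline SD, the gain against change scores can fall to a few percent.

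The gap touches supportive effect sizes and any optional intervals or p-values. It does not touch the primary non-inferiority conclusion or the superiority test on the composite. It is an improvement worth making, not the correction of an invalid analysis.

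**What to change.** In 10.9, for the continuous ODI, VAS leg, VAS back and SF-12 scores:

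- Make the between-group estimate the Month-60 difference with 95% interval, adjusted for the baseline score. Use ANCOVA, or a repeated-measures model with baseline, treatment, visit, treatment-by-visit and site. The repeated-measures model also uses the earlier scores of patients who miss Month 60.
- Run it on the mITT set and say so, because 10.4 assigns secondary efficacy analyses to the per-protocol set and the two sections should agree.
- Base any optional p-value on this estimate.
- Keep the descriptive tables and the ODI and VAS responder rates.
- Add a sensitivity analysis that does not treat the missing Month-60 scores of patients exited under 9.3 as missing at random, for example by imputing worse scores for them over a stated range.

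The cost is SAP wording, modest extra programming and that one sensitivity analysis. No new data are needed.
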